### **2.7.1 Adverse events**

#### **2.7.1.1 Coding of adverse events**

Adverse events will be coded using the latest version of MedDRA terminology at the time of DBL.

### **2.7.1.2 General rules for AE reporting**

All information obtained on AEs will be displayed by treatment group and subject.

The number (and percentage) of subjects with TEAEs (events started after the first dose of study medication, or events present prior to start of double-masked treatment but increased in severity based on PT) will be summarized in the following ways:

- By treatment, primary SOC and PT.
- By treatment, primary SOC, PT and maximum severity.
- By treatment, pre-defined topic of interest, primary SOC and PT.

Separate summaries will be provided for study medication-related AEs, serious adverse events (SAEs), and other significant AEs leading to discontinuation.

A subject with multiple adverse events within a primary SOC is only counted once towards the total of the primary SOC.

### **2.7.1.3 Treatment-emergent adverse events**

AE summaries will include all TEAEs. TEAEs are defined as AEs starting on or after the first day of study treatment. All AEs will be listed. AEs starting prior to the first day of study treatment (non-TEAEs) will be flagged in the listings.

All TEAEs will be summarized by study phase as defined in [Section 2.1.1](#).

TEAEs will be summarized by presenting the number and percentage of subjects having at least 1 TEAE, having at least 1 TEAE in each primary SOC, and for each PT using MedDRA coding.

A subject with multiple occurrences of a TEAE will be counted only once in the AE category.

Separate summaries will be presented by SOC, PT and severity. A subject with multiple severities for an AE will be summarized under the worst severity recorded for the event.

Any information collected will be listed as appropriate.

### **2.7.1.4 Adverse event summaries**

The following summary tables will be provided:

- AEs, regardless of study treatment relationship, by primary SOC, PT and maximum severity
- Most frequent ( $\geq 5\%$ ) AEs, regardless of study treatment relationship, by PT
- AEs, related to study treatment reported by investigator, by primary SOC and PT
- SAEs, regardless of study treatment relationship, by primary SOC and PT
- SAEs, related to study treatment reported by investigator, by primary SOC and PT
- SAEs occurring with a frequency of  $\geq 0.5\%$ , regardless of study treatment relationship, by PT
- SAEs, regardless of study treatment relationship, by primary SOC, PT, and seriousness criteria
- AEs leading to discontinuation, regardless of study treatment relationship, by primary SOC and PT

- AEs requiring dose adjustment or study treatment interruption, regardless of study treatment relationship, by primary SOC and PT
- AEs requiring additional therapy, regardless of study treatment relationship, by primary SOC and PT
- Death resulting from AEs, regardless of the study treatment relationship, by primary SOC and PT

#### **2.7.1.5 Adverse events of special interest / grouping of AEs**

Separate summaries will be provided for AEs related to all angioedema, elevated creatinine, hyperkalemia, symptomatic hypotension. The summaries will be presented by primary SOC, PT and worst severity.

In addition, suspected or confirmed SARS-CoV-2 infections will be listed.

Additionally, a sensitivity analysis will be performed on the AESIs for subjects randomized to sacubitril/valsartan. The number and percentages of AESIs occurring prior to the active dose of sacubitril/valsartan will be presented along with the number and percentages of AEs of special interest occurring on or after the active dose of sacubitril/valsartan during the study. The following definitions will be used:

Angioedema:

*AE prior to active study treatment = if event occurred within 1 day of dosing as recorded on the Angioedema Assessment Visit 2 (randomization)*

*AE after active study treatment = if event occurred after 1 day of dosing as recorded on the Angioedema Assessment Visit 2 (randomization)*

Symptomatic hypotension:

*AE prior to active study treatment = First dose date  $\leq$  event*

*AE after active study treatment = event  $\leq$  Last dose date of medication*

Elevated creatinine:

*AE prior to active study treatment = First dose date:time of study treatment  $\leq$  event*

*AE after active study treatment = event  $\leq$  Last dose date:time of medication*

Hyperkalemia:

*AE prior to active study treatment = First dose date:time of study treatment  $\leq$  event*

*AE after active study treatment = event  $\leq$  Last dose date:time of medication*

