#### 2.1.1 General definitions

##### Study treatment/ study drug

- Participants recruited under the Protocol Version 00 (Original Protocol) received either sacubitril/valsartan or valsartan during the first 8 weeks of the study.

- Participants recruited under the amended protocols (01 to 04) will receive either sacubitril/valsartan or valsartan during the approximately 84 weeks of the study.
- Participants recruited under Protocol Version 00 (Original Protocol) and who have not completed the double-blind period are eligible to continue in Amendment 01 with no open-label period.

Study treatment or study drug will refer to either of these 2 drugs.

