## **2.7 Safety analyses**

For all safety analyses, the SAF will be used. All listings and tables will be presented by treatment group and in-hospital/out-of-hospital randomization category.

Safety summaries (tables, figures) include only data from the on-treatment period with the exception of Baseline data, which will also be summarized where appropriate (eg, change from Baseline summaries). In addition, a separate listing for death including on-treatment and post treatment deaths will be provided. In particular, summary tables for AEs will summarize only on-treatment events, with a start date during the on-treatment period (treatment-emergent AEs (TEAEs)). The on-treatment period lasts from the date of first administration of study treatment to the last study visit.

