#### **2.7.4.6 Angioedema**

Data collected from the Questionnaire for Angioedema-Like Event at Screening, Randomization and Follow-up visits will be summarized. Separate summaries will be produced for all angioedema events. The number and percentage for categorical variables and summary statistics for continuous variables of the following will be presented by visit, treatment group and open-label sacubitril/valsartan:

- Outcome (Not recovered/Not resolved, Recovered/Resolved, Recovering/Resolving, Recovered/Resolved with Sequelae, Fatal, Unknown)

- Duration of angioedema in days [*end date – start date + 1*]
- Timing of event (After first dose, after multiple doses, dose not given) [not asked at screening]
  - Study medication discontinued due to event (No, Yes, Unknown)
  - Event occurred within 1 day of dosing (Within 1 day of dose but less than or equal to 1 hour, within 1 day of dose but greater than 1 hour, After 1 day of dosing, Unknown)
- History of prior angioedema or angioedema like event (No, Yes, Unknown)
  - If yes, medications taken at time of previous event:
    - ACE inhibitor (No, Yes, Unknown)
    - ARB (No, Yes, Unknown)
    - Renin inhibitor (No, Yes, Unknown)
    - Other medications (No, Yes, Unknown)
- Presence of hereditary angioedema (No, Yes, Unknown)
- Any family members with history of angioedema-like events (No, Yes, Unknown)
- Signs and symptoms for current event
  - Shortness of breath/dyspnea (No, Yes, Unknown)
  - Difficulty swallowing/dysphagia (No, Yes, Unknown)
  - Difficulty speaking/dysarthria (No, Yes, Unknown)
  - Pain on swallowing/odynophagia (No, Yes, Unknown)
  - Stridor (No, Yes, Unknown)
  - Abdominal pain (No, Yes, Unknown)
  - Other (No, Yes, Unknown)
- Edema present (No, Yes)
  - Periorbital edema (No, Yes, Unknown)
  - Head edema (No, Yes, Unknown)
  - Neck edema (No, Yes, Unknown)
  - Lip edema (No, Yes, Unknown)
  - Tongue edema (No, Yes, Unknown)
  - Throat edema (No, Yes, Unknown)
  - Submandibular edema (No, Yes, Unknown)
  - Genitalia edema (No, Yes, Unknown)
  - Extremities edema (No, Yes, Unknown)
  - Other (No, Yes, Unknown)
- Previous edematous episodes (No, Yes, Unknown)
  - Number of previous edematous episodes
- ACEi taken in the past (No, Yes, Unknown)
- ACEi taken during trial participation after Screening (No, Yes, Unknown) [not asked at Screening]

- Dose changed within 2 days of event (No, Yes, Unknown)
- ARB taken in the past (No, Yes, Unknown)

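### The single-arm table of adverse events of special interest cannot separate events before the active dose from events on or after it, because its printed rules overlap or are mislabelled

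*SAP*

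**What the plan says.** SAP 2.7.1.5 adds a sensitivity analysis restricted to subjects randomized to sacubitril/valsartan. Its aim is clear: "The number and percentages of AESIs occurring prior to the active dose of sacubitril/valsartan will be presented", next to those occurring on or after that dose. Definitions then follow for each event.

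- **Angioedema.** Before: "AE prior to active study treatment = if event occurred within 1 day of dosing", as recorded on the Visit 2 assessment. After: more than 1 day from dosing, on the same form.
- **Elevated creatinine and hyperkalemia.** The 'prior' line begins "AE prior to active study treatment = First dose date:time of study treatment" and requires this to be at or before the event. The 'after' line requires the event to be at or before the last dose date and time.
- **Symptomatic hypotension.** The same pair of inequalities, using dates without times.

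Three other parts of the SAP bear on how these should read. Section 2.7.4.6 lists the angioedema form items, including "Event occurred within 1 day of dosing (Within 1 day of dose but less than or equal to 1 hour" and a separate item, "Timing of event (After first dose, after multiple doses, dose not given". Section 2.7.1.3 says "TEAEs are defined as AEs starting on or after the first day of study treatment". Section 2.7 says "The on-treatment period lasts from the date of first administration of study treatment to the last study visit".

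**The concern.** A before/after table needs two classes that do not overlap and that meet at the active dose. For three of the four events, the printed lines look like the two halves of a single on-drug interval (first dose ≤ event ≤ last dose) given opposite labels. For angioedema, the cut lies one day after dosing, and the side nearest the dose is called 'prior'.

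If programmed literally, the table would report on-drug hypotension, creatinine and potassium events as having preceded active sacubitril/valsartan. The same holds for angioedema recorded at Visit 2 within a day after a dose. Separating pre-drug from on-drug events is the table's only purpose, and the error runs towards making drug-period events look like background.

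**Working it through.** **Is there a placebo-only period that would make the first day of dosing pre-active?** None is described. Under Protocol 6.1, each patient takes the assigned active tablet together with placebo matching the other drug, twice daily. SAP 1.1 places the ACE-inhibitor washout before randomization. SAP 2.1.1 says that Version 00 participants "received either sacubitril/valsartan or valsartan during the first 8 weeks of the study", and the corresponding statement for the amendments covers about 84 weeks. The genuine pre-dose window is therefore informed consent to first dose, during which adverse events are already collected (Protocol 10.1.1).

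**Hypotension, creatinine, hyperkalemia.** Let F be first dose, L last dose and E event onset. The printed rules are:

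- prior: F ≤ E
- after: E ≤ L

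Take F = day 1, L = day 100 and last visit = day 130 as an example. The correct column follows the table's stated aim and the on-treatment period in SAP 2.7.

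| Event day | F ≤ E | E ≤ L | Printed result | Correct |
|---|---|---|---|---|
| −3 | no | yes | after only | prior |
| 1 | yes | yes | both | on/after |
| 50 | yes | yes | both | on/after |
| 100 | yes | yes | both | on/after |
| 115 | yes | no | prior only | on/after |

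Correctly and uniquely placed: 0 of 5. The result does not depend on the days chosen. Over all days from 30 before first dose to 30 after last dose, with L = day 56, all 56 on-drug days meet both rules, the 30 earlier days meet only 'after', and the 30 later days meet only 'prior'. With L = day 588, the counts are 588, 30 and 30.

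**Could it be a sign or label slip?** No simple reversal restores the split.

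- Reverse both signs (E ≤ F; E ≥ L): events between F and L fall in neither class.
- Reverse the first only (E ≤ F; E ≤ L): pre-dose events fall in both.
- Reverse the second only (F ≤ E; E ≥ L): on-drug events before L are 'prior' only.
- Swap the labels: the two ends come right, but on-drug events still meet both rules.

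**Angioedema.** The timing field in SAP 2.7.4.6 has four categories:

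| Category | Printed label | Correct |
|---|---|---|
| Within 1 day, up to 1 hour after dose | prior | on/after |
| Within 1 day, more than 1 hour after dose | prior | on/after |
| After 1 day | after | on/after |
| Unknown | no rule | to be specified |

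Two of the four are labelled 'prior' although both follow a dose. The item that would identify a pre-dose event (dose not given) is not used. The rule cites only the Visit 2 form, so events recorded at follow-up visits have no rule either.

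**Illustrative size.** The SAP states no denominator and the documents give no event counts. Assume subjects as denominator, 450/2 = 225 in the arm, and no pre-dose events. The correct 'prior' figure is then 0/225 = 0.0%. For one of the three inequality-based events, the printed rules give:

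- 11 subjects with an on-drug event: 11/225 = 4.9% shown as 'prior'
- 22 subjects: 22/225 = 9.8%
- 45 subjects: 45/225 = 20.0%

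The same percentage appears in the 'after' column each time.

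**After the correction** (prior: E < F; on/after: E ≥ F), every day falls in exactly one class: 30 prior and 86 on/after with L = day 56; 30 and 618 with L = day 588.

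**The case against.** The strongest reply is that this is a drafting slip in a minor table. It is descriptive, single-arm and untested. The sentence introducing it states the intended split, so a competent programmer would notice. The limited scope is true and is reflected in the verdict. But a silent correction would leave the table at odds with the plan, and a literal one would give a false table.

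A second point is that SAP 2.7 restricts safety summaries to on-treatment data, and 2.7.1.3 sends earlier events to flagged listings. Under those general rules a pre-dose column would be empty. The explicit request for such a column in 2.7.1.5 is the more specific instruction, so it should govern. The point still stands to this extent: the corrected text should state the exception.

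Third, the angioedema rule covers only the Visit 2 form, and 'dosing' could mean the first or the most recent dose. Both are fair. If it means the first dose, only events in about the first day are mislabelled. If it means the most recent dose, twice-daily dosing would put almost any on-drug event recorded there within a day. The label is wrong under either reading.

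Finally, Version 00 is not among the documents, so its regimen is known only through the SAP. Even an assumed placebo lead-in would not help, because no printed rule contains the time of the first active dose.

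**Conclusion.** The concern holds: the rules are wrong as written and fail for all four events. For hypotension, creatinine and hyperkalemia, the two classes overlap throughout dosing and are reversed outside it. For angioedema, the classes do not overlap, but the cut-point and the 'prior' label are wrong. This follows from the printed text alone. The percentages are illustrations that depend on the stated assumptions, not estimates.

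The impact is limited to this one table. The between-arm logistic analysis (SAP 2.6.2.7), the treatment-emergent tables (2.7.1.3), the exposure-adjusted rates (2.7.1.6) and the angioedema questionnaire summary (2.7.4.6) do not use these rules. It should be corrected, but no efficacy or comparative safety conclusion depends on it.

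**What to change.** Replace the event-specific definitions in SAP 2.7.1.5 with one rule for all four events:

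- **Prior:** onset before the first dose of study treatment.
- **On/after:** onset from the first dose to the end of the on-treatment period as defined in SAP 2.7.
- Use date and time where collected, otherwise date. Count a same-day event without a time as on/after, in line with 2.7.1.3. A timed event earlier on the first-dose day would be prior here but treatment-emergent there; say so in a footnote.
- **Angioedema:** events within 1 day after a dose, and events recorded at any post-dose visit, count as on/after. Events at Screening, or marked as dose not given with onset before first dose, count as prior. Classify an unknown timing category by onset date.
- State that the denominator is subjects, and that the pre-dose column is a deliberate exception to the on-treatment-only rule.

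If the sponsor sees no use for a consent-to-first-dose column, deleting the table would also remove the error. The cost is one SAP paragraph and one table program. No new data are needed.

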#### **2.7.1.6 Exposure Adjusted Adverse Events**

The following Exposure adjusted incidence rate of adverse events will be presented by study phase and treatment group:

- Exposure-adjusted incidence rate of adverse events by preferred term

- Exposure-adjusted incidence rate of study treatment related adverse events by primary system organ class and preferred term
- Exposure-adjusted incidence rate of adverse events leading to permanent study treatment discontinuation by primary system organ class and preferred term
- Exposure-adjusted incidence rate of serious adverse events by primary system organ class and preferred term
- Exposure-adjusted incidence rate of deaths by primary system organ class and preferred term

The exposure adjusted incidence rate (IR) will be derived by the number of subjects with an event divided by the corresponding sum of the exposure duration for all subjects, where duration of exposure in Subject Treatment Years (STY) is counted up to the first qualifying event (or end of time at risk for subjects without event).

Incidence rate will be set to the 100 STY and only on treatment events (TEAE) will be included.

### **2.7.2 Deaths (EAC Adjudicated)**

All subject deaths will be adjudicated by EAC. Subject deaths will be summarized by total (all-cause), primary cause of death, type of cardiovascular death and type of non-cardiovascular death and will be presented by study phase (see [Section 2.1.1](#) for study phase definitions). A subject listing of all deaths with recorded principal cause of death will be provided. All subjects in the SAF will be included for the above analysis.

- A KM curve will be presented for all-cause deaths.

### **2.7.3 Laboratory data**

All laboratory data will be listed by treatment group, in-hospital/out-of-hospital randomization, subject, and visit/time and if normal ranges are available abnormalities will be flagged.

Shift tables using the low/normal/high/ classification will be used to compare Baseline to the worst post Baseline value. The number and percentage of subjects with laboratory values will be presented by low/normal/high (low and high) classifications to compare Baseline to worst post Baseline value.

In addition, laboratory values and the change from Baseline for each parameter by visit will be summarized by treatment group sacubitril/valsartan. In the event that there are multiple laboratory values within a visit, the worst value will be summarized.

A summary of hyperkalemia labs by visit will also be presented by treatment group. The highest potassium value for the event and any potassium re-test results will be descriptively summarized. Similarly, creatinine labs will also be presented by visit, treatment group. The highest creatinine value for the event and any creatinine re-test results will be descriptively summarized.

Listings of all laboratory values will be provided. Separate listings for hyperkalemia labs, creatinine labs, and pregnancy tests will also be provided. Any notable laboratory abnormalities will also be flagged.

### **2.7.3.1 Laboratory Assessments**

#### **Hematology**

Hemoglobin, hematocrit, red blood cell (RBS) count, white blood cell (WBC) count with differential (Basophils, Eosinophils, Lymphocytes, Monocytes, Neutrophils, Bands, Other (absolute value preferred, %s are acceptable), and platelet count will be measured at Visits 1, 2, 7, 11, 13, 15, and 17 (central lab). Hemoglobin A1c will be measured at Visit 2 and 17 (central lab).

#### **Chemistry**

Assessments required for eligibility that need to be measured at Visit 1 include creatinine, potassium, and total bilirubin. Blood urea nitrogen (BUN), glucose, creatinine, total bilirubin, AST (SGOT), ALT (SGPT), alkaline phosphatase, sodium, potassium, chloride, calcium, total protein, albumin, uric acid, and lipid profile be measured at Visits 1 (local lab), 2, 3, 5, 7, 9, 11, 13, 15, 16 and 17 (central lab).

#### **Urinalysis**

Dipstick-test determination of specific gravity, pH, blood, total protein, bilirubin, ketones, and leukocytes will be measured at Visit 2 (central lab). If dipstick is positive, a qualitative microscopic determination, including WBCs high power field and RBCs high power field will be performed.

#### **Pregnancy Test**

All female subjects of childbearing potential will have a serum pregnancy test (hCG) performed at Visit 1 (local lab). In addition, these subjects will have a urine pregnancy test conducted in the local laboratory at Visits 2, 5, 7, 11, 13, 15, 16, and 17. If any of these tests are positive at Visits 1 and 2, the subject should not be enrolled in the trial. If a subject should become pregnant during the trial, the subject may remain in the trial for follow-up visits but must discontinue study drug.

### **2.7.4 Other safety data**

#### **2.7.4.1 Electrocardiogram and cardiac imaging data**

A standard 12 lead ECG will be performed by Visit 1. ECG data will be collected at Visit 1 will also be listed along with the summary statistics.

#### **2.7.4.2 Vital signs**

All vital signs (SBP and diastolic blood pressure (DBP) (mmHg), pulse rate (sitting/beats per minute), weight (kg), height (cm), BMI (kg/m^2) and waist/hip circumference) will be descriptively summarized at each visit by treatment group. Change from Baseline will also be presented, excluding height and waist/hip circumference.

A separate summary table will be presented with the number and percentages of subjects having notable vital signs based on changes relative to Baseline values (see [Section 2.1.1](#) for study phase definitions and [Section 5.3.3](#) for the list of notable vital signs).

The number and percentages of subjects having symptomatic hypotension will also be summarized. The following variables associated with symptomatic hypotension will also be presented: symptoms occurring while standing, any treatment or medication change as a result of episode, lowest documented SBP, SBP position, lowest documented DBP and DBP position. A listing for symptomatic hypotension will also be presented.

#### **2.7.4.3 Heart Failure Event**

Any new HF event information will be collected and listed. The following will be presented:

- Type of event (HF hospitalization [hospital stay  $\geq$ 24 hours], HF ED visit, Urgent/unplanned HF office visit, Worsening HF during the index hospitalization [qualifying HF event], None of the aforementioned types occurred with, or apply to, this HF event)
- Symptoms of worsening HF (Dyspnea – [Dyspnea at rest, Dyspnea on exertion, Orthopnea, Paroxysmal nocturnal dyspnea, Tachypnea], Decreased exercise tolerance [reduced ability to perform activities that induce physical exertion due to dyspnea or fatigue], Fatigue [lack of energy, extreme tiredness, inability to complete usual activities], Worsening end-organ perfusion – [Confusion (thought to be from low cardiac output), Reduced urine output], Symptoms of volume overload – [Lower extremity swelling, Increased abdominal distension]), Other)
- Physical exam signs of worsening HF (Peripheral edema, Increased abdominal distension or ascites [in the absence of hepatic disease], Pulmonary rales/crackles, Elevated jugular venous pressure and/or hepatojugular reflux, New or worsening 3rd heart sound, Clinically significant weight gain thought to be related to fluid retention [ $>3$  to 4 lbs. in 3 to 4 days], Other)
- Laboratory evidence of worsening HF (Increased NT-proBNP [ $> 2,000$  pg/mL], Radiographic evidence of pulmonary congestion, Right heart catheterization with pulmonary capillary wedge pressure  $\geq 18$  mmHg, central venous pressure  $\geq 12$  mmHg, or a cardiac index of  $< 2.2$  L/min/m^2, Other)
- Increased or additional therapy (No, Yes, Unknown)
  - Therapy type (Augmentation of oral diuretic therapy with additional diuretic; Initiation of intravenous diuretic; Uptitration of intravenous therapy, if already on therapy; Initiation of inotrope, or vasodilator therapy; Initiation of percutaneous mechanical circulatory support; Initiation of temporary surgical support [extracorporeal membrane oxygenation or temporary surgical ventricular assist device ie, centrimag]; Implantation of durable left ventricular assist device; Listed for heart transplantation)
  - Evidence of cardiogenic shock (No, Yes, Unknown)
  - Blood sample collected for BNP or NT-proBNP (No, Yes, Unknown)
    - BNP result (pg/mL)
    - NT-proBNP result (pg/mL)
  - Contributors/precipitants of worsening HF (Medication nonadherence, Dietary indiscretion, Acute coronary syndrome, Other systemic illness – [Respiratory infection, Urinary tract infection, Other])

